7.2 Subject Selection

7.2.1 Inclusion Criteria

Subjects are required to meet all of the following inclusion criteria in order to be enrolled in the study. For lesion characteristics, each target lesion must meet eligibility. A maximum of two (2) target lesions may be treated per subject; target lesions may be in the same limb or in different limbs.

General Inclusion Criteria

1. Age of subject is \geq 18 years.
2. Subject is able and willing to comply with all assessments in the study.
3. Subject or subject's legal representative has been informed of the nature of the study, agrees to participate, and has signed the approved consent form.
4. Estimated life expectancy $>$ 1 year.
5. Rutherford Clinical Category 2, 3, 4 or 5 of the target limb(s).

Angiographic Inclusion Criteria

6. One or two target lesion(s) located in a native de novo superficial femoral, popliteal or infrapopliteal artery (above the ankle joint), in one or both limbs.

 SHOCKWAVE <small>MEDICAL INC</small>	No.: CP 67398	REV. C
	TITLE: FORWARD PAD IDE Study Protocol	
	CLASS: CLINICAL PROTOCOL	PAGE 21 OF 65

7. Target lesion reference vessel diameter (RVD) between 2.0 mm and 7.0 mm by investigator visual estimate.
8. Target lesion stenosis $\geq 70\%$ (for vessels below the knee, defined as P3 to the ankle joint) or $\geq 90\%$ (for vessels above the knee) by investigator visual estimate.
9. Target lesion length is ≤ 150 mm by investigator visual estimate. Target lesion can be all or part of the 150 mm treated zone.
10. Calcification is at least moderate defined as presence of fluoroscopic evidence of calcification: 1) on parallel sides of the vessel and 2) extending $> 50\%$ the length of the lesion if lesion is ≥ 50 mm in length; or extending for minimum of 20mm if lesion is < 50 mm in length.

7.2.2 Exclusion Criteria

Subjects who meet any of the following exclusion criteria may not be enrolled in the study:

General Exclusion Criteria

1. Rutherford Clinical Category 0, 1 and 6 (target limb).
2. History of endovascular or surgical procedure on the target limb within the last 30 days, or planned within 30 days of the index procedure, with the exception of toe amputation. Note: inflow treatment of non-target lesions is allowed providing successful treatment.
3. Subject in whom antiplatelet or anticoagulant therapy is contraindicated.
4. Subject has known allergy to contrast agents or medications used to perform endovascular intervention that cannot be adequately pre-treated.
5. Subject has known allergy to urethane, nylon, or silicone.
6. Myocardial infarction within 60 days prior to enrollment.
7. History of stroke within 60 days prior to enrollment.
8. Subject has acute or chronic renal disease with eGFR < 30 ml/min/1.73 m² (using CKD-EPI formula), unless on renal replacement therapy.
9. Subject is pregnant or nursing.
10. Subject is participating in another research study involving an investigational agent (pharmaceutical, biologic, or medical device) that has not reached the primary endpoint.
11. Subject has other medical, social or psychological problems that, in the opinion of the investigator, preclude them from receiving this treatment, and the procedures and evaluations pre- and post-treatment.
12. Covid-19 diagnosis within 30 days.

 SHOCKWAVE <small>MEDICAL INC</small>	No.: CP 67398	REV. C
	TITLE: FORWARD PAD IDE Study Protocol	
	CLASS: CLINICAL PROTOCOL	PAGE 22 OF 65

13. Planned use of cutting/scoring balloons, re-entry or atherectomy devices in target lesion(s) during the index procedure.
14. Planned major amputation of target limb.
15. Acute limb ischemia.
16. Occlusion of all the inframalleolar outflow arteries/vessels (i.e., desert foot).
17. Subject already enrolled into this study.

Angiographic Exclusion Criteria

18. Failure to successfully treat clinically significant inflow lesions in the ipsilateral iliac, femoral, or popliteal arteries, defined as ≤30% residual stenosis with no serious angiographic complications (e.g. embolism).
19. Failure to successfully treat significant non-target infrapopliteal lesions, if treated prior to treatment of target lesion(s). Successful treatment is defined as obtaining ≤50% residual stenosis with no serious angiographic complications (e.g., embolism).
20. Target lesion includes in-stent restenosis.
21. Evidence of aneurysm or thrombus in target vessel.
22. No calcium or mild calcium in the target lesion.
23. Target lesion within native or synthetic vessel grafts.
24. Failure to successfully cross the guidewire across the target lesion; successful crossing defined as tip of the guidewire distal to the target lesion in the absence of flow limiting dissections or perforations.

7.3 Informed Consent

Prior to undergoing any study-specific tests or procedures, the subject or their legally authorized representative must sign and date the site's current and approved Institutional Review Board (IRB) informed consent form (ICF) in order to be eligible for study participation. The informed consent must contain all elements required by 21 CFR Part 50 and ISO 14155:2020 and comply with the ethical principles of ICH/GCP and the Declaration of Helsinki.

7.3.1 Process for Obtaining Informed Consent

The process for obtaining informed consent is outlined below:

- The Investigator or his/her authorized designee conducts the informed consent process
- All aspects of the clinical study that are relevant to the subject's decision to participate will be included in the consent form
- Investigators will avoid any coercion or undue improper influence on, or inducement of, the subject to participate
- The consent process shall not waive or appear to waive the subject's legal rights

 SHOCKWAVE <small>MEDICAL INC</small>	No.: CP 67398	REV. C
	TITLE: FORWARD PAD IDE Study Protocol	
	CLASS: CLINICAL PROTOCOL	PAGE 23 OF 65

- The consent must use native non-technical language that is understandable to the subject
- The Investigator or designee will provide ample time for the subject to read and understand the informed consent form and to consider participation in the clinical investigation
- The consent must include personally dated signatures of the subject and the Investigator, or an authorized designee responsible for conducting the informed consent process, and/or all signatures required by the reviewing IRB
- The Investigator or designee will provide the subject with a copy of the signed and dated informed consent form and any other written information
- The informed consent process should be documented by the Investigator completing the consenting process in the subject's institutional medical record

7.3.2 Subjects Needing Legally Authorized Representative

Informed consent may be given by a legally authorized representative only if a subject is unable to make the decision to participate in a clinical study. In such cases, the subject shall also be informed about the clinical study within his/her ability to understand.

Please follow the local IRB guidelines on this process.

7.3.3 Subjects Unable to Read or Write

Informed consent shall be obtained through a supervised oral process if a subject or legally authorized representative is unable to read or write, if allowed by the IRB. An independent witness shall be present throughout the process. The written informed consent form and any other information shall be explained to the prospective subject or his/her legally authorized representative and, whenever possible, either shall sign and personally date the informed consent form. The witness also signs and personally dates the informed consent form attesting that the information was accurately explained, and that informed consent was freely given.

7.3.4 Addition of New Information

Shockwave Medical will revise the written informed consent form whenever new information becomes available that may be relevant to the subject's confirmed participation in the study. The revised information will be sent to the Investigator for approval by the IRB. After approval by the IRB, a copy of this information must be provided to the participating subjects, and the informed consent process as described above needs to be repeated.

Please follow the local IRB guidelines on the process of re-consenting subjects.

7.4 Schedule of Events and Evaluations

Table 1 lists the schedule of events and evaluations required for the study.

 SHOCKWAVE <small>MEDICAL INC</small>	No.: CP 67398	REV. C
	TITLE: FORWARD PAD IDE Study Protocol	
	CLASS: CLINICAL PROTOCOL	PAGE 24 OF 65

Table 1. Schedule of Events and Evaluations

Assessment	Screening / Baseline	Enrollment and Procedure	Discharge ¹	30 Days (-7/+14 days)	6 Month (180±30 days)	12 Month (360±30 days)
Eligibility	✓					
Informed Consent ²	✓					
Medical History	✓					
Physical Exam	✓			✓	✓	✓
eGFR	✓					
Pregnancy Test	✓ ³					
Medications	✓		✓	✓	✓	✓
ABI or TBI	✓ ⁴			✓	✓	✓
Rutherford Category	✓			✓	✓	✓
Angiogram or IVUS		✓				
DUS						✓
Adverse Events		✓	✓	✓	✓	✓
ABI = ankle-brachial index; TBI = toe-brachial index 1. Within 12-24 hours post procedure or prior to hospital discharge, whichever occurs first 2. Consent to be obtained within 30 days prior to procedure. 3. Within seven (7) days of the procedure for women of child-bearing age. 4. Within 60 days prior to procedure.						

7.5 Medications

Anticoagulation/antiplatelet medications should be administered according to the 2017 European Society of Cardiology (ESC) and European Society of Vascular Surgery (ESVS) PAD guidelines [20] and the 2016 American College of Cardiology (ACC) and American Heart Association (AHA) PAD guidelines [5].

Additional recommendations for anticoagulation and antiplatelet medications include:

- Unfractionated heparin dosing should be undertaken according to hospital standard of care.
- Prasugrel or ticagrelor may be used as an alternative to clopidogrel for existing management of acute coronary syndrome (ACS).

 SHOCKWAVE <small>MEDICAL INC</small>	No.: CP 67398	REV. C
	TITLE: FORWARD PAD IDE Study Protocol	
	CLASS: CLINICAL PROTOCOL	PAGE 25 OF 65

- Follow antiplatelet and anticoagulation guidelines for the management of patients with atrial fibrillation.

7.6 Screening/Baseline Procedures

Baseline assessments must be completed within 30 days of the procedure with the exception of ankle-brachial index (ABI) and toe-brachial index (TBI), which can be completed within 60 days of the procedure, and a pregnancy test which must be done within seven (7) days of the procedure for women of child-bearing age. Informed consent must be obtained prior to any study-specific evaluations needed to assess eligibility which are not considered standard of care. Subjects on warfarin or direct thrombin inhibitors should be followed per institutional standard of care by the physician.

Baseline assessments include:

- Medical history
- Physical examination
 - Vital signs
 - Height and weight
- eGFR (if needed, for patients with acute or chronic renal disease)
- Review of anticoagulation/antiplatelet medications
- ABI or TBI of target limb (at rest; use same test for subject throughout study)
- Rutherford Category of target limb
- Urine pregnancy test if female of child-bearing age

Note: If treatment of two target lesions is planned across both limbs, the RC category, ABI, and TBI for each limb must be assessed. If ABI cannot be assessed due to non-compressible vessels, this should be documented. If TBI is used, subject should have TBI at each follow-up visit.

7.7 Index Procedure

The IVL procedural flow diagram is described in the steps below and illustrated in **Figure 2**.

All devices used during the index procedure should be recorded including IVL catheters and adjunctive devices (if required). Up to two (2) target lesions may be treated per subject. If the distal portion of the target lesion extends beyond the ankle joint, treatment using the JAVELIN IVL Catheter is allowed if the Investigator deems it clinically necessary to optimize the procedure outcome.

The JAVELIN configuration, FLX or XTR, may be chosen at the Investigator's discretion. Crossover to the other configuration is allowed if needed per the IVL procedural steps outlined below.

Information on usability will be collected to help understand how operators perceive information from the JAVELIN IVL Catheter, interpret the information and make decisions about what to do, and how to manipulate the device.

[figure not shown]

Figure 2. JAVELIN IVL Treatment Algorithm

 SHOCKWAVE <small>MEDICAL INC</small>	No.: CP 67398	REV. C
	TITLE: FORWARD PAD IDE Study Protocol	
	CLASS: CLINICAL PROTOCOL	PAGE 27 OF 65

7.7.1 Procedural Imaging Requirements

An angiographic cine will be obtained at four (4) timepoints for each target lesion as follows:

1. Pre-procedure (include run-off the foot)
2. Post-JAVELIN (immediately following treatment with JAVELIN and before post-dilatation)
3. Post-Dil (following mandatory post-dilatation)
4. Final (end of procedure, include run-off to the foot)

If any non-target lesions are treated, an additional cine will be obtained prior to IVL treatment of any target lesion(s) to ensure no serious angiographic complications have occurred and that the patient still meets criteria to be enrolled. All angiographic images must be submitted to the core lab for analysis. If intravascular imaging (including IVUS or OCT) is performed as standard of care, images from the four timepoints (pre-procedure, post-JAVELIN, post-dil and final) should be submitted to the Sponsor for analysis.

Core lab training materials will be provided with detailed instructions on the image acquisition process.

7.7.2 Assessment of Calcification

To meet eligibility, there must be fluoroscopic evidence of calcification: 1) on parallel sides of the vessel and 2) extending > 50% the length of the lesion if lesion is ≥ 50 mm in length; or extending for minimum of 20mm if lesion is < 50 mm in length.

The 1st required angiographic cine (Pre-procedure) should be acquired following assessment of calcification.

7.7.3 Treatment of Non-Target Lesions

Non-target lesions should be treated successfully prior to treatment of the target lesion(s) whenever possible. Non-target lesions distal to the target lesion(s) or found after target lesion is treated may be treated after the target lesion(s).

Non-target lesions may be treated with any commercially available device; treating a non-target lesion with a device that is unapproved or considered investigational will result in a protocol deviation.

Clinically significant inflow lesions in the ipsilateral iliac, femoral, or popliteal arteries must be treated with $\leq 30\%$ residual stenosis and no serious angiographic complications (e.g. embolism). Significant non-target infra-popliteal lesions should be treated with $\leq 50\%$ residual stenosis with no serious angiographic complications (e.g., embolism). If there are serious angiographic complications following treatment of non-target lesions prior to insertion of the JAVELIN IVL Catheter, the patient should not be enrolled.

 SHOCKWAVE <small>MEDICAL INC</small>	No.: CP 67398	REV. C
	TITLE: FORWARD PAD IDE Study Protocol	
	CLASS: CLINICAL PROTOCOL	PAGE 28 OF 65

7.7.4 Definition of Enrollment

The definition of enrollment is when the subject signs informed consent, meets all general and angiographic eligibility criteria, a 0.014" guidewire has crossed the target lesion, and the JAVELIN IVL Catheter has been inserted over the guidewire and into the body.

7.7.5 Catheter Delivery & Crossover (if required)

If the Investigator is able to pass a guidewire but is unable to deliver the JAVELIN IVL catheter to the proximal edge to the target lesion, an adjunctive tool may be used prior to re-insertion of the JAVELIN IVL Catheter. Allowable adjunctive tools include guide catheter, guide extension catheter, buddy wire or buddy balloon, and PTA balloon. Atherectomy, cutting/scoring balloons, and specialty crossing devices should not be used. All adjunctive tools used during the procedure should be documented.

If the JAVELIN IVL Catheter still cannot be delivered to the proximal edge of the target lesion, the user may cross over to the other JAVELIN IVL Catheter configuration (XTR or FLX depending on which configuration was used first). All crossovers should be documented.

If the user is unable to advance any JAVELIN IVL Catheter to the proximal edge of the target lesion after crossing over to the alternate JAVELIN IVL configuration, this is considered an **IVL Device Failure**. Treatment should continue per standard of care for the subject.

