7.7.6 Pre-IVL Dilatation of Target Lesion & Crossover (if required)

If the operator is unable to cross the JAVELIN IVL Catheter through the entire length of the target lesion, a standard PTA balloon up to 2.5 mm may be used for pre-dilatation of the target lesion prior to treatment with the JAVELIN IVL Catheter. All efforts should be made to pass the JAVELIN IVL Catheter prior to use of a standard PTA balloon.

If the operator is unable to pass the JAVELIN IVL Catheter after pre-dilatation, the operator may attempt to cross with the alternate JAVELIN IVL Catheter configuration (crossover). Note: if the operator has already used the alternate configuration (prior crossover per Section 7.7.5), a second crossover is not permitted. All crossovers should be documented.

If the user is unable to advance any JAVELIN IVL Catheter across the target lesion, this is considered an **IVL Device Failure**. Treatment should continue per standard of care for the subject.

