7.7.10 Destination Therapy

Destination therapy is allowed at the discretion of the Investigator. Destination therapy may include commercial IVL, bare-metal stent (BMS), drug-eluting stent (DES), drug coated balloon (DCB) or Tack implant.

 SHOCKWAVE <small>MEDICAL INC</small>	No.: CP 67398	REV. C
	TITLE: FORWARD PAD IDE Study Protocol	
	CLASS: CLINICAL PROTOCOL	PAGE 30 OF 65

A. BMS, DES, DCB or Tack implant is allowed for the following PTA failures:

- Residual stenosis \geq 50% by visual estimate, or
- Un-resolved flow-limiting (\geq Grade D) dissection, or
- Trans-lesional gradient >10 mm Hg is observed.

If this treatment is performed at the time of procedure, it is considered standard of care to maximize acute luminal gain and does not meet the definition of serious deterioration in the SAE definition (Section 10.1.2).

All dissection Type/Grade A, B, and C must be documented as an adverse event. Dissection Type/Grade D, E, and F must be documented as a SAE.

The 4th and final required angiographic cine should be acquired after all endovascular procedures on the target lesion are complete.

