4.2. Primary Effectiveness Endpoint

The primary effectiveness endpoint is **Technical Success** defined as final residual stenosis $\leq 50\%$ without flow-limiting dissection (\geq Grade D) of the target lesion by angiographic core lab.

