4.3. Secondary Endpoints

- **Serious angiographic complications** defined as flow-limiting dissection (\geq grade D), perforation, distal embolization, or acute vessel closure as assessed by the angiographic core lab.
- **IVL Technical Success (post-dil)** defined as *post-dilatation* residual stenosis $\leq 50\%$ without flow-limiting dissection (\geq Grade D) of the target lesion by angiographic core lab (measured immediately following mandatory post-dilatation).
- **IVL Device Success** defined as the ability to deliver, advance across the target lesion, pressurize, pulse, flush and retrieve the JAVELIN IVL Catheter.
- **Technical Success (final)** defined as *final* residual stenosis $\leq 30\%$ without flow-limiting dissection (\geq Grade D) of the target lesion by angiographic core lab.
- **MAE** at 6 and 12 months (as a composite and individual components)
- **Primary Patency** at 12 months defined as:
 - Above the knee lesions: freedom from $\geq 50\%$ restenosis as determined by Duplex Ultrasound (DUS) and freedom from Clinically-Driven Target Lesion Revascularization (CD-TLR)
 - Below the knee lesions: freedom from both total occlusion (100% diameter stenosis by DUS) in all of the target lesions in a flow pathway, as well as a CD-Revascularization (CD-TLR).

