Clinical endpoints include repeat revascularization procedures on target lesions/vessels, death, target limb amputations, and safety endpoints including Major Adverse Events, that occur within a specific time period. For each reporting period, the event rate will be defined as the number of subjects experiencing the event divided by the number of evaluable subjects. A subject will be considered evaluable for a reporting period if the study day of last contact is at or after the lower limit of the reporting window on the snapshot date. Acceptable study contacts include a study visit, adverse event, CEC adjudicated event date, image date, or other verifiable event that occurs during the active follow-up of a subject. Active follow-up ends when a subject completes the study, withdraws consent, or is considered lost to follow-up.

B. Core Lab Endpoints

Core lab endpoints include the endpoints that are determined by core lab assessment (duplex ultrasound or angiography), such as restenosis measured by duplex ultrasound or residual stenosis by angiography. Core lab endpoints rely on the actual evaluable assessment. If the scheduled assessment is not completed or the data are not evaluable (i.e., not readable or non-diagnostic), it will be treated as missing value and excluded from the analysis. Data will be used for subjects who have an evaluable (readable or diagnostic) scheduled duplex ultrasound.

C. Determination of Primary Patency Composite Effectiveness Endpoint

Primary patency contains both core lab endpoint (by visit) and clinical/safety endpoint (by cut-off days); the event of the individual component will be determined first, and the composite endpoint will then be determined.

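### The SAP has no rule for lesions that JAVELIN cannot reach or cross: Technical Success scores them on the result after rescue, and IVL Technical Success (post-dil) can drop them or credit another treatment

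*Protocol*

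**What the plan says.** - **Enrollment.** Protocol 7.7.4 counts a subject as enrolled when, among other conditions, "the JAVELIN IVL Catheter has been inserted over the guidewire and into the body". This comes before the catheter reaches the lesion. Protocol 9.4 takes all enrolled subjects as the intent-to-treat population. SAP section 8 takes the first 90 evaluable subjects and does not define that word for angiographic effectiveness.
- **Device failure.** Protocol 7.7.5 covers a catheter that cannot be brought to the lesion even after a switch of configuration: this is an IVL Device Failure, and "Treatment should continue per standard of care for the subject". Protocol 7.7.6 covers crossing: "If the user is unable to advance any JAVELIN IVL Catheter across the target lesion, this is considered an" IVL Device Failure, with the same instruction for further care.
- **Primary effectiveness.** SAP 4.2 has Technical Success "defined as final residual stenosis" of 50% or less without a dissection of Grade D or worse, read by the core lab. Protocol 7.7.10 places the final cine after all work on the lesion. On what that work may involve it says: "Destination therapy may include commercial IVL, bare-metal stent (BMS), drug-eluting stent (DES), drug coated balloon (DCB) or Tack implant". The definition does not require that JAVELIN was delivered or pulsed. The secondary endpoint at 30% has the same structure.
- **Post-dil endpoint.** SAP 4.3 has IVL Technical Success (post-dil) "measured immediately following mandatory post-dilatation". It does not mention lesions that JAVELIN did not treat.
- **Missing core lab data.** For an assessment that was not done or cannot be read, SAP Appendix A states: "it will be treated as missing value and excluded from the analysis".
- **Where the failure is recorded.** IVL Device Success (SAP 4.3) requires delivery, crossing, pulsing and retrieval. It is secondary and has no hypothesis or performance goal.

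**The concern.** The SAP's objective (section 2) is to show the effectiveness of the JAVELIN catheter against performance goals. Protocol 3.1.3 presents the device as an option for very narrow channels that challenge other devices. Reaching and crossing the lesion is therefore part of what is being claimed.

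A lesion in which JAVELIN could not be used, later opened by other means, enters the primary as a success. That is a coherent procedural result, but a reader cannot tell from the rate how much of it came from JAVELIN.

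The post-dil endpoint is the more serious gap because its name attributes the result to IVL. Under the text as it stands, a true device failure either leaves the denominator or is scored on what another treatment achieved. At stake is how the effectiveness rates in the 510(k) submission are read, and whether the scoring of these lesions is fixed before the pooled results are seen.

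**Working it through.** **Inputs.** From SAP 6.2 and 6.3: goal 85.0%, expected rate 97.0%, one-sided exact binomial test at 0.025, 90 subjects, effectiveness power 98.1%. The documents give no device-failure rate *f*, so a range is assumed. One lesion per subject (90 lesions) is also assumed, although up to two are allowed and Protocol 9.2.2 analyses per lesion.

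**Step 1: reproduce the plan's figure.** P(X ≥ 84 | 90, 0.85) = 0.0131 and P(X ≥ 83 | 90, 0.85) = 0.0308, so the pass mark is 84. P(X ≥ 84 | 90, 0.97) = 0.9812, which matches 98.1%. No stated figure is wrong.

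**Step 2: follow a device-failure lesion through each endpoint.**

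| Endpoint | Situation | Scored as |
|---|---|---|
| Technical Success (primary) | rescue reaches ≤50%, no Grade D or worse | success |
| Technical Success (primary) | rescue does not | failure, because of the final result |
| IVL Technical Success (post-dil) | no readable post-dil cine | excluded as missing |
| IVL Technical Success (post-dil) | post-dil cine after non-JAVELIN treatment | by that result |
| IVL Device Success | either | failure |

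The SAP's evaluable wording might instead remove the subject from the primary cohort. That route would not count a failure either.

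**Step 3: fixed counts.** Bounds are lower limits of the two-sided 95% Clopper-Pearson interval, which matches the 0.025 test. Suppose 87 of 90 lesions end as successes and *k* of the 87 were rescued device failures.

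- As written, any *k*: 87/90 = 96.7%, bound 90.6%, pass.
- Failures counted, *k* = 3: 84/90 = 93.3%, bound 86.1%, still above 85%.
- Failures counted, *k* = 4: 83/90 = 92.2%, bound 84.6%, below 85%.
- Post-dil endpoint, *k* = 4, assuming post-dil status equals final status in the other 86 lesions: 83/86 = 96.5% if the four are dropped, and 83/90 = 92.2% if they are kept as failures. The difference is 4.3 points.

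**Step 4: chance of clearing 85% with failures counted.** With 97% success in crossed lesions, p = 0.97 × (1 − *f*), and the pass mark stays at 84/90.

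| *f* | p | P(X ≥ 84) |
|---|---|---|
| 0% | 0.9700 | 98.1% |
| 2% | 0.9506 | 84.3% |
| 3% | 0.9409 | 71.8% |
| 5% | 0.9215 | 43.4% |
| 10% | 0.8730 | 5.1% |

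**Step 5: sensitivity to the assumptions.** The primary as written keeps its 98.1% at every *f* only if rescued lesions also succeed 97% of the time. At *f* = 10% with 80% rescue success, p = 0.9 × 0.97 + 0.1 × 0.80 = 0.953 and the chance of passing is 86.9%. With 60% rescue success, p = 0.933 and it is 60.1%. With 110 lesions the pass mark is 101, and the 5% row of Step 4 becomes 64% instead of 43%.

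**The case against.** The strongest reply is that the plan already separates three layers: device performance (IVL Device Success), the result after post-dilatation, and the procedural result (Technical Success). The primary does not carry IVL in its name. Its benchmark in SAP 5.2 and Appendix B is also a final-stenosis rate, and the consensus definition cited in SAP 5.2 is read at the end of the procedure. All of this stands, and it is why the primary should stay as it is.

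It also rules out some stronger readings that a reader might infer:

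- *That the failure is hidden.* It is not; IVL Device Success reports it.
- *That the trial passes however often JAVELIN fails.* A failed rescue counts against the primary through the final result, as Step 5 shows.
- *That the primary should become crossed-and-successful, tested against 85%.* Nothing in the documents shows that the benchmark sources scored non-crossing as failure. Part of the fall in Step 4 comes from changing the endpoint while keeping the goal, the 97% and the 90.
- *That any commercial device may be used for rescue.* Protocol 7.7.5 advises against atherectomy, cutting or scoring balloons and specialty crossing devices during delivery. It does not say whether that carries over after a device failure.

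Two limits remain. The post-dil reading rests on the SAP's silence together with its general missing-data rule. Figure 2, the treatment algorithm, is not shown and could not be checked. Neither supplies a scoring rule, so the gap in the SAP text remains.

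**Conclusion.** The concern holds as an attribution and scoring gap, not as an error in the primary endpoint or its power. The primary is a defensible procedural measure that does not by itself show JAVELIN's contribution. IVL Technical Success (post-dil) does need a rule, because the text now allows a device failure to be excluded or to be scored on a non-JAVELIN result.

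In the illustration, four rescued device failures among 87 successes separate a bound of 90.6% from one of 84.6%, and raise the post-dil rate by 4.3 points if they are dropped. The chance that an analysis counting failures clears 85% is 84%, 72%, 43% and 5% at device-failure rates of 2%, 3%, 5% and 10%. These figures assume 90 lesions and 97% success in crossed lesions. They are a range, not a forecast.

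**What to change.** In SAP 4.3, section 10 and Appendix A:

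1. For IVL Technical Success (post-dil), keep every lesion in which JAVELIN was attempted in the denominator. Score each IVL Device Failure as a failure, not as missing and not by the result of another treatment.
2. Leave the primary as it is. Pre-specify a supplementary analysis that scores IVL Device Failure lesions as Technical Success failures, and report it with its exact confidence bound beside the 85% goal. State the bound's level. Protocol 9.2.2 reports a one-sided 95% bound while the test is at 0.025; the bounds above match the test.
3. List separately the lesions rescued by commercial IVL or a stent.

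The cost is SAP wording, settled before the pooled results are analysed. The protocol already calls for crossovers, adjunctive tools and all devices used to be recorded, and for four cines per lesion. The reported post-dil rate may be a few points lower. No change to patient care is proposed.
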